8.0 DEVICE DESCRIPTION

All implant components to be used in this trial have been approved for sale and use throughout Australia.

In addition, Stryker's Robotic Arm, comprising of surgical arm guidance module and cameras will be used for intraoperative assessment of implant and limb position. This system is commercially available, and has been approved for sale and use throughout Australia.

8.1 Device Trade Name

The Restoris® MCK Multicompartmental Knee System

The **Restoris® MCK Multicompartmental Knee System** is a commercially available, ARTG listed device. The Restoris® MCK Multicompartmental Knee System is manufactured by MAKO Surgical Corp. [name].

The prosthetic components under study in this protocol include:

- RESTORIS® MCK Multicompartmental Knee System
 - RESTORIS® MCK Femoral Condyle

<http://ssp.intranet/sites/raqa/qms/documents/FM-CRD-029.docx>

MAKORCT-15 Final version 5.0 22 February 2018

- RESTORIS® MCK Patellofemoral
- RESTORIS® MCK Tibial base plate
- RESTORIS® MCK Tibial insert only
- RESTORIS® MCK Patella Dome (cemented)

Figure 1: The RESTORIS® MCK system, Family of implants

The components of the RESTORIS® MCK system are used to individually treat the components of the knee when showing osteoarthritis. The medial unicompartmental and patellofemoral components may be combined to perform a bicompartamental knee arthroplasty. These surgical options are shown below in Figure 2.

Bicompartamental

Figure 2: Stryker robotic-arm assisted surgery solutions.

Figure 3: The Mako System consists of the RIO® Surgical Arm, RIO® Guidance Module, and the Camera as pictured. The system utilizes tactile robotic arm technology with integrated intelligent surgical instruments and navigation visualization system to pre-plan and treat each patient uniquely. After the implant plan is confirmed the system prevents resection outside of the defined spatial boundaries through an established relationship between the cutting burr and the patient's anatomy. The end effector of the robotic arm is controlled by the surgeon as shown while the system provides the surgeon with real-time visual, tactile and auditory feedback.[7]

Figure 4: Surgeon holding Stryker's Robotic Arm

The comparator (Stryker Triathlon Primary Total Knee System) group:

The **Stryker Triathlon Primary Total Knee System** is a commercially available, ARTG listed device. The Triathlon Primary Total Knee System is manufactured by Stryker Orthopaedics (Mahwah, New Jersey).

The prosthetic components to be implanted as part of this study will collectively be referred to as the **Stryker Triathlon Primary Total Knee System**. Within this system, various

individual implants of different designs, sizes and thicknesses are included. The required components to be used in this study group include:

- CR Femoral Cementless Component – Beaded with Peri-Apatite
- CR Femoral Cemented Component
- Primary Tibial Baseplate – Cemented
- CR Tibial Insert – X3
- CS Tibial Insert – X3
- Triathlon X3 Patella (cemented asymmetric/symmetric)

Figure 3: The Triathlon® Knee system, Family of implants

In addition, the **Stryker Precision Knee Navigation System**, comprising of computer hardware and software and associated instrumentation, will be used for intra-operative assessment of implant and limb position. This system is a commercially available, TGA (Therapeutic Goods Administration) listed device, and has been approved for sale and use throughout Australia.

8.2 Device Supply

All device components will be supplied by the local supplier in Australia in accordance with usual commercial supply.

The Restoris® MCK Multicompartmental Knee System, Triathlon Primary Total Knee System, and Precision Navigation System are supplied by Stryker Australia Pty Ltd.

9.0 SURGICAL PROCEDURES

The Restoris® MCK Multicompartmental Knee System will be implanted using the corresponding instrumentation systems supplied by the manufacturer, as approved for use with this system, and as described in the surgical technique provided by the manufacturer (Appendix 1).

The Triathlon Primary Total Knee System will be implanted using the corresponding instrumentation system supplied by the manufacturer, as approved for use with this system, and as described in the surgical technique provided by the manufacturer (Appendix 2).

Appropriate post-operative care will be given and is at the discretion of the physician.

10.0 INFORMED CONSENT

The Investigator will inform the patient of the purpose of the study, proposed duration of the study, follow-up schedule, method of application and randomisation of study groups. The Investigator will discuss foreseeable risks involved, as well as potential benefits that result from the use of the device. The Investigator will also inform all patients that, should an unanticipated adverse device-related effect occur during the study which, in their opinion presents unreasonable risks to the patients, all patients will be notified and patient enrolment will be terminated. Patient information will be used during the analysis of the results of the clinical study but the confidentiality of the patient will be maintained at all times.

The patients will be informed by the Investigator that they are free to refuse participation in this Investigation; and if they should participate, that they may withdraw from the study at any time without compromising further medical care.

A signed and dated Informed Consent must be obtained by the Investigator or his/her designee from the patient prior to enrolment into this study. The original signed and

dated information sheet and patient consent will be kept by the Investigator. A copy will be provided to the patient.

11.0 EVALUATIONS

All data will be recorded on Case Report Forms or via Electronic Data Capture (EDC). The surgeon or study coordinator will complete and sign forms at the time of each protocol required visit.

The following data will be collected for all patients:

- **Patient Demographics:** A record of the patient's date of birth, gender, height, and weight will be obtained pre-operatively.
- **Medical History:** Relevant medical history will be recorded pre-operatively.
- **Surgical Details:** A summary of the surgical procedure will be collected during the operation. This will include details of the prosthetic components implanted, operating time and comments.
- **Patient outcome measurements:** Surgeon assessment of patient clinical outcomes will be recorded at various study visits. The following outcome scores will be recorded at time points as set out in the patient evaluation schedule. These include pre-operative, 6 week, 3 month, 12 month and 24 month follow-up visits (see Appendix 3):
 - **Oxford Knee Score (OKS):** A 12 item questionnaire was developed to measure outcomes of patients undergoing total knee replacement (Dawson et al. 1998). The score is a self-completed questionnaire that asks patients to answer questions on their pain levels and function (Whitehouse et al. 2005).
 - **EQ-5D Euro-Qol (EQ-5D-5L):** The EQ-5D-5L is a standardised patient-completed instrument for use as a measure of health outcome (Fransen and Edmonds, 1999). It consists of 5 dimensions: mobility, self care, usual activities, pain/discomfort, and anxiety/depression. There are 5 levels of severity to select from within each dimension.

- **VAS Pain:** A graphic Visual Analogue Scale (VAS) used as measurement instrument for patients to indicate their level of pain. The amount of pain that a patient feels is believed to range across a continuum from none to an extreme amount of pain i.e. from the patient's perspective this spectrum appears continuous - their pain does not take discrete jumps, as a categorization of none, mild, moderate and severe (Wewers et al. 1990).
- **Forgotten Joint Score (FJS):** The Forgotten Joint Score is a newly-developed twelve-item, self-reported assessment of how aware recipients of hip and knee joint replacement are of their joint in everyday life (Behrend et al, 2011). These scores have been further validated to demonstrate reproducibility when repeated (Roe et al, 2014). A computer-adaptive test version called FJS-CAT has been developed from the original version which consists of a reduced test length, and had a strong level of acceptance by patients when administered (Giesinger et al. 2013)
- **New Knee Society Score (KSS):** A validated score assessing surgeon generated objective measures based on technical outcomes such as ROM, alignment and stability, and subjective measures based on patient satisfaction, patient expectations and functional activity of the knee (Noble et al. 2012), (Scuderi et al. 2012).
- **Radiographs:** A MAKO CT Arthrogram or MAKO CT will be used for surgical planning and study purposes. Anteroposterior (A/P), and Lateral Knee radiographs will be obtained pre-operatively and ≤5 days postoperatively for immediate assessment. Anteroposterior (A/P), and Lateral knee post-operative radiographs will also be collected 3 months, 12 months and 24 months, as outlined in the Patient Evaluation Schedule. Skyline knee x-rays will be obtained pre-operatively and at 12 months and 24 months post-operatively. The pre-operative radiographs will be compared to radiographs taken post-operatively for assessment of implant positioning and

cartilage wear. All radiographs will be independently reviewed and assessed to quantify any radiographic changes within the region of the study device.

Outlined below are the specifications required for the radiographic images as per the Patient Evaluation Schedule.

A/P Knee: To be performed as a weight bearing A/P x-ray using a 24x30 or 35x43 cassette plate at a 100cm FFD. When using a CR system, please ensure magnification is defaulted to 100%. Coverage to include 3cm above the patella and 3cm below the tibial tuberosity. X-rays collected post op ≤5 days post-surgery will not be performed as weight bearing.

Lateral Knee: To be performed as a weight bearing lateral x-ray using a 24x30 or 35x43 cassette plate at a 100cm FFD. When using a CR system, please ensure magnification is defaulted to 100%. Coverage to include 3cm above the patella and 3cm below the tibial tuberosity. X-rays collected post op ≤5 days post-surgery will not be performed as weight bearing.

Skyline Knee: To be performed in the supine position with the knee flexed at 45 degrees using a 24x30 cassette plate at a 100cm FFD. When using a CR system, please ensure magnification is defaulted to 100%. Coverage to include whole patella and trochlear groove.

- **Adverse Events:** All information on general medical, operative and device related complications will documented and tabulated (see section 19.0 for Adverse Event description and handling).

12.0 STATISTICAL METHODS

12.1 Enrolment and Randomisation

At least **35** patients per study group will be enrolled. Enrolment is defined as meeting the study Inclusion and Exclusion criteria.

<http://sspintraneet/sites/raqa/qms/documents/FM-CRD-029.docx>

MAKORCT-15 Final version 5.0 22 February 2018

The randomisation procedure by which the Knee System for the individual operation will be chosen (**Restoris® MCK Multicompartmental Knee System** versus the **Triathlon Primary Total Knee System**) will be centrally organised for all investigators, and allocated via block randomisation. At the time the patient meets the Inclusion and Exclusion criteria to take part in the study, the surgeon or designee will use the central randomisation system (via Inform) to obtain a randomised allocation. The block randomisation scheme will be performed using randomisation software with a block size of **4**. The randomisation scheme will ensure that during the enrolment period the ratio of the number of cases in the two groups remains approximately constant and that surgical kits are available for each case.

12.2 Sample Size Justification

The change in the Oxford Knee Score (OKS) from pre-op to post-op assessments has a standard deviation of approximately 8.0 (Scott et al, SD=9.8; Walker et al, Table 2, SD=6 for UKR, and SD=8 for TKR). The parameters of the sample size calculation were set as follows: level of significance 0.05, 2-sided test, and postulated difference and standard deviation of 6.0 and 8.0 respectively. For these settings a sample of 29 patients in each arm is required to achieve a power of 80%. The sample size was increased by 20% to 35 in each arm, so 70 in total, in order to allow for withdrawals.

12.3 Data Capture and Analysis

At the commencement of the study, data may be recorded on 2-part NCR paper Case Report Forms (CRFs). Electronic Data Capture (EDC) will be implemented for this study, at which time the sponsor will enter all paper data collected to date and all new patient data will be captured via EDC. Investigators and study coordinators will be trained on EDC completion.

The surgeon or designated signatory will complete and sign forms at the time of completion.

Original paper CRFs will be collected by Stryker for data entry. Copies will remain at the Investigator site. Archiving will be undertaken in accordance with ICH/GCP guidelines (Appendix 5).

Any unclear or ambiguous data will be queried, either via paper queries or electronic queries as applicable and all cleaned data will be analysed.

12.4 Statistical Analysis

For each treatment group the demographic data will be summarised as number of observations, mean, standard deviation, minimum, median, maximum for continuous variables such as age, and as frequency and percentage for categorical variables such as gender.

For the test of the treatment effect the null hypothesis is no difference between the means of the 2 treatment groups, and will be tested against the alternative hypothesis that there is a difference between the means of the treatment groups.

The primary and continuous secondary efficacy variables will be analysed with a mixed model for repeated measurements (MMRM). The model will include factors for treatment group, time, and the interaction between treatment group, and time. For each variable the baseline values will be included in the model as covariate. The treatment effect will be tested against between patient variance. The time effect, and the interaction between treatment group and time will be tested against within patient variance. The results will be summarised as mean, and 95% CI by treatment group, and time. The least squares means will be reported for the treatment difference at each time, and overall with 95% CI. The results will be presented in tabular format, and graphically by treatment group, and time. The continuous variables of change from baseline, and percentage change from baseline will be reported as mean, and 95% CI for each treatment group.

Adverse events will be tabulated separately and reviewed for any commonalities.

The data will be summarised and comparisons presented according to:

<http://sspnet/sites/raqa/qms/documents/FM-CRD-029.docx>

MAKORCT-15 Final version 5.0 22 February 2018

- Treatment group : Restoris® MCK Multicompartmental Knee System or Triathlon Primary Total Knee System
- Adverse events: General complications, local complications, device-related complications, revisions/removals, loosening and pain.

In the event of errors in randomisation, the patient will be classified according to the treatment received. All randomisation inconsistencies will be listed.

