3.0 OBJECTIVES

PRIMARY

The primary objective of this study is:

- To compare the clinical outcomes of Knee Replacement surgery using the Oxford Knee Score (OKS) at 24 months, in patients receiving Bicompartamental Knee Replacement using Restoris MCK Multicompartmental Knee System with Stryker's robotic-arm assisted surgery system Mako, to Total Knee Replacement using the Triathlon Total Knee System performed with Stryker's robotic-arm assisted surgery system Mako.

SECONDARY

The secondary objectives of this study are:

- To determine functional and clinical outcomes of Bicompartamental Knee Replacement (BKR) and Total Knee Replacement (TKR) (including pain, function and health-related quality of life) with Restoris MCK Multicompartmental Knee System and Triathlon Primary Total Knee System at 24 months via:
 - EQ-5D: The EQ-5D is a standardised instrument for use as a measure of health outcome.
 - VAS Pain: A graphical Visual Analog Scale that patients use to indicate their level of pain.
 - New Knee Society Score 2011 (KSS): A validated score assessing surgeon generated objective measures based on technical outcomes, and subjective measures based on patient satisfaction, patient expectations and functional activity of the knee (Noble et al. 2012) (Scuderi et al. 2012).
 - Forgotten Joint Score (FJS): The Forgotten Joint Score is a newly-developed twelve-item, self-reported assessment of how aware recipients

of hip and knee joint replacement are of their joint in everyday life (Behrend et al, 2011).

- To compare incidence of loosening, reoperation and revision in patients receiving Restoris MCK Multicompartmental Knee System, compared to Triathlon Total Knee System.
- To determine length of hospital stay in patients receiving Restoris MCK Multicompartmental Knee System, compared to Triathlon Total Knee System.

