6.1 Inclusion Criteria

1. The patient is a suitable candidate for a Bicompartamental Knee Replacement and has moderate to severe patellofemoral wear and medial compartment wear (surgeons discretion)
2. The patient has no fixed flexion greater than 10 degrees.
3. The patient has maximal flexion greater than 100 degrees
4. The patient has a passively correctable varus deformity
5. The patient has a functionally Intact ACL.
6. The patient has no significant patellofemoral malalignment
7. The patient has negligible lateral compartment degeneration with no appreciable loss of cartilage height (surgeon's discretion).
8. The patient has pain that is not localised to the medial compartment only
9. The patient is a male or non-pregnant female.
10. The patient has signed the study specific, HREC-approved, Informed Consent document and is willing and able to comply with the specified pre-operative and post-operative clinical and radiographic evaluations.

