7.0 STUDY DESIGN

This is a prospective, randomised, study with patients treated at multiple hospitals.

Prior to each surgeon enrolling their first study patient, they must be accredited to perform Stryker's Robotic-arm Assisted Surgery. Accreditation includes attending a Surgical Skills training course provided by Stryker and led by a surgeon experienced with using Mako, review of the planning and surgical technique guides, surgical observation and consultation with current Mako users.

All potential study patients will be assigned a MAKORCT-15 study ID.

If a patient has previously had a MAKO CT Arthrogram and wishes to participate in the study, the patient is required to sign the study approved consent form and the previous MAKO CT Arthrogram will be used for study purposes.

If the patient has previously had a MRI or MRI/CT Arthrogram (within 6 months of planned study surgery date), the patient is required to sign the study approved consent form and the previous MRI or MRI/CT Arthrogram will be used for study purposes. Once the study consent form is signed, the patient will be referred for a MAKO CT for surgical planning purposes.

If a patient has not had a MAKO CT Arthrogram, MRI or MRI/CT Arthrogram and wishes to participate in the study, the patient is required to sign the study approved consent form, and once signed the patient will be referred for a MAKO CT Arthrogram.

<http://ssp.intranet/sites/raqa/qms/documents/FM-CRD-029.docx>

MAKORCT-15 Final version 5.0 22 February 2018

If the patient meets the Inclusion and Exclusion criteria and has signed the study consent form, the patient will be enrolled onto the study. If the patient does not meet the Inclusion and Exclusion criteria and has signed the study consent form, the patient will be terminated from the study as a Screen Failure.

Enrolled patients will be randomised to one of two equally sized groups either; the Restoris® MCK Multicompartmental Knee System group or the Triathlon Primary Total Knee System group. Randomisation will take place via the Investigator or designee using the central randomisation system within Inform for allocation to either group. Block randomisation will be performed by a statistician using specialised randomisation software with a block size of 4.

Any deviation from the assigned treatment will be reported as a deviation from Protocol.

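### Does the repeated-measures model need a hospital term because patients are treated at several hospitals?

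*Combined protocol and SAP*

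**What the plan says.** Section 7.0 describes the setting: "This is a prospective, randomised, study with patients treated at multiple hospitals". Neither the number of hospitals nor any measure of how much outcomes differ between them is given.

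Section 12.1 says that the allocation "will be centrally organised for all investigators, and allocated via block randomisation", with a block size of 4. No stratification factor is named.

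Section 12.4 lists the model terms: "The model will include factors for treatment group, time, and the interaction between treatment group, and time". The baseline value of each variable is a covariate. On the error term it says: "The treatment effect will be tested against between patient variance". No hospital, site or surgeon term appears in Section 12.

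Section 12.2 takes a difference of 6.0, an SD of 8.0, a two-sided level of 0.05 and 80% power, giving 29 per arm, raised to 35 per arm for withdrawals. The SD is stated for the change in Oxford Knee Score from before to after surgery.

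**The concern.** In a multicentre trial one looks for centre in the model. Two features suggest that hospitals could differ. In Section 6.1 the degree of wear that qualifies a patient is left to the surgeon. Section 9.0 says of aftercare: "Appropriate post-operative care will be given and is at the discretion of the physician". Local practice could bear particularly on length of stay, which is a comparative secondary objective: "To determine length of hospital stay in patients receiving Restoris MCK Multicompartmental Knee System, compared to Triathlon Total Knee System".

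If hospitals differ and the model ignores it, that variation inflates the variance against which treatment is tested. With 29 analysed patients per arm giving only just 80% power, even a small loss of precision seems worth avoiding. A worse possibility would be a test that does not hold its level.

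**Working it through.** **1. The plan's own figure.** For a two-sample t-test, SE = SD × √(2/n) = 8 × √(2/29) = 2.10, and 6/2.10 = 2.86. The noncentral t distribution with 56 degrees of freedom gives 80.1% power at 29 per arm and 78.7% at 28. So 29 reproduces, and 29 × 1.2 = 34.8 gives the 35.

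**2. Is the test valid without the term?** Individual patients are allocated without regard to hospital. A hospital effect is then one more component of the variation between patients. It enters the true variance of the treatment difference and the variance estimated from the data alike, so the planned standard error is right on average. Simulation agrees. Settings: 70 randomised on one shared list of blocks of 4, 58 analysed, 2, 4 or 6 equal hospitals, baseline covariate, four post-operative visits, visit correlation 0.6, 10,000 runs. Type I error without the hospital term is 4.6% to 5.2%. A simpler layout with one 24-month measurement (2,500 runs, Monte Carlo error about 0.4 points) gives 4.1% to 5.9%, with no trend towards inflation.

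**3. The most a hospital term could gain.** If a share ρ of the variance lay between hospitals and could be removed perfectly, the SE would be 2.10 × √(1 − ρ):
- ρ = 5%: 2.05 (2.5% lower)
- ρ = 10%: 1.99 (5.1% lower)
- ρ = 20%: 1.88 (10.6% lower)

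**4. What it gains in practice.** Hospital effects must be estimated from few hospitals, so the gain is smaller. The second and third columns come from the planned-form simulation, adding a random hospital intercept (REML, Kenward-Roger). The share is an assumption throughout.

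| Hospital share | Fall in SE | Power change, SD 8 after baseline adjustment | Power change, SD 6.69 |
|---|---|---|---|
| 0% | – | -0.5 to 0.0 | – |
| 5% | 0.4–0.7% | +0.2 to +0.6 | about +0.3 |
| 10% | 2.2–2.3% | +1.6 to +1.9 | about +1.1 |
| 20% | 4.2–6.8% | +3.2 to +5.0 | +2.0 to +3.1 |

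In the single-measurement layout the SE is 0.2% to 0.9% worse with the term at shares of 0% to 2%, and 0.2% to 0.5% better at 5%.

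**5. Why the last column is the fairer one.** Section 12.2 gives 8 as the SD of change, but the model in 12.4 adjusts for baseline. With equal variances before and after surgery and correlation r between them, the variance of change is 2σ²(1 − r) and the variance given baseline is σ²(1 − r²). The ratio of SDs is therefore √((1 + r)/2). The documents do not give r; assumed values:
- r = 0.3: SD 6.45, power at 29 per arm 93.6%
- r = 0.4: SD 6.69, power 91.8%
- r = 0.5: SD 6.93, power 90.0%

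The last column takes r = 0.4 and applies the SE reductions of the second column to the noncentral t calculation. On this assumption the baseline covariate already supplies far more precision than a hospital term could add.

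**The case for a change.** The best case for the term is that it costs almost nothing: at most 0.5 points of power if hospitals do not differ, and a zero variance estimate returns the planned model. If hospitals do differ clearly, it returns a few points. The design may also have less margin than step 5 suggests. Section 12.2 itself cites an SD of 9.8, at which an unadjusted comparison with 29 per arm has only 63% power, and a 20% loss from 35 leaves 28.

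The low cost is real, but it does not turn an option into a correction. The range of SDs is uncertainty about variation between patients, which a hospital term does not settle. Section 4.0 provides for extra recruitment to replace withdrawals, and 35 analysed per arm would give 87.1% power even at SD 8. The grounds for expecting large hospital differences are thin as well: the discretion in Sections 6.1 and 9.0 belongs to individual clinicians, who need not map onto hospitals. Accreditation (7.0), robotic assistance in both arms (1.0) and the manufacturers' surgical techniques (9.0) all work against such differences. With two hospitals, the between-hospital variance would rest on one degree of freedom.

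Length of stay is the stronger example, because it has no baseline value to absorb hospital differences. In a single-measurement layout the SE falls by 0.1–0.4%, 1.5–1.9% and 4.4–5.8% at shares of 5%, 10% and 20%; a skewed outcome was not examined. But length of stay is recorded once and does not fit the repeated-measures model, and Section 12.4 names no other analysis for it. There is no specified model from which a hospital term is missing.

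If lists were in fact kept per hospital, the test without the term would be conservative at a high share: 3.6% to 4.5% at 20%, and 4.5% to 4.8% at 10%. The documents do not say that lists are kept this way. Even then the type I error would not be inflated.

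**Conclusion.** The concern does not hold. With individual randomisation through a central scheme and no stated stratification by hospital, the model in Section 12.4 gives an unbiased comparison at its nominal level without a hospital term. The possible benefit is precision only: nil or slightly negative at a hospital share of about 0% to 2%, under 1 point of power at 5%, about 1 to 2 points at 10%, and 2 to 5 points at 20%, depending on the SD after baseline adjustment. No document gives a share, and none shows that it is large. Experienced statisticians could reasonably choose a random intercept, a fixed factor or nothing for a trial of 70 patients.

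This rests on reading Section 12.1 as one shared list, on 2 to 6 hospitals, and on simulations with complete data and a patient random intercept; an unstructured visit covariance and intermittent missing visits were not examined. The argument from patient-level randomisation in step 2 does not depend on these figures. The conclusion covers the absent hospital term only, not other features of Sections 12.4 and 12.5.

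### As written, the repeated-measures model uses one baseline slope for every visit from 6 weeks to 24 months; a baseline-by-time term would protect the precision of the 24-month OKS contrast at almost no cost

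*Combined protocol and SAP*

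**What the plan says.** Section 12.4 applies one mixed model for repeated measurements to the primary and the continuous secondary variables. Its terms are given in two sentences: "The model will include factors for treatment group, time, and the interaction between treatment group, and time", and then "For each variable the baseline values will be included in the model as covariate". Treatment-by-time is the only interaction named, there or elsewhere.

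The model's output is described as follows: "The least squares means will be reported for the treatment difference at each time, and overall with 95% CI". The primary objective in section 3.0 concerns one of those times: "To compare the clinical outcomes of Knee Replacement surgery using the Oxford Knee Score (OKS) at 24 months". Section 11.0 gives the assessment points ("These include pre-operative, 6 week, 3 month, 12 month and 24 month follow-up visits"), and the evaluation schedule in section 1.0 confirms that OKS is collected at all of them. The model therefore has four post-operative OKS values per patient.

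**The concern.** The plan lets the treatment effect differ at each visit but, on a plain reading, lets pre-operative OKS act through a single coefficient. That is an extra assumption: a patient's pre-operative score would have to predict early recovery at 6 weeks and the settled result at 24 months with the same slope. The plan neither states nor justifies this.

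If it fails, the fitted slope is a compromise across the four visits, and the 24-month contrast is over- or under-adjusted. Baseline adjustment has some work to do here: there are 35 patients per arm, and randomisation is described only as blocks of 4, with no stratification by pre-operative OKS. What is at stake is precision. Part of any chance imbalance in pre-operative OKS stays in the 24-month difference as added variance.

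**Working it through.** **The plan's own figure.** Section 12.2 sets "level of significance 0.05, 2-sided test" and "postulated difference and standard deviation of 6.0 and 8.0 respectively". The noncentral t calculation gives power 0.787 at 28 per arm and 0.801 at 29, so the stated 29 is reproduced. Then 29 × 1.2 = 34.8, rounded up to 35. Nothing below changes that number.

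**Inputs.** From the documents: 35 per arm, 1:1 allocation, four post-operative OKS visits, difference 6.0, and SD of change 8.0 (sources cited at 6, 8 and 9.8). Assumed, because the documents do not give them: baseline SD 8, residual SD 7, equal residual correlation between visits (0.3 to 0.7), complete data, and the slopes in the table.

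**Formulas.** Under these assumptions:
- The common slope is the mean of the four visit slopes.
- Slope error e = 24-month slope − common slope.
- The 24-month difference is the raw difference minus the common slope times the baseline imbalance, so it carries a leftover of e × imbalance.
- Standard error of the imbalance = 8 × √(2/35) = 1.91 points.
- Variance with the right slope = 49 × 2/35 = 2.80; with the common slope = (49 + 64e²) × 2/35.
- Variance ratio = 1 + 64e²/49.
- Implied SD of change at 24 months = √(64 × (1 − 24-month slope)² + 49).

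| Slopes at 6 wk, 3, 12, 24 mo | Common slope | Size of e | Variance ratio | Leftover per 1-SE imbalance (points) | Implied SD of change | Power, common slope |
|---|---|---|---|---|---|---|
| .5, .4, .3, .25 | 0.3625 | 0.1125 | 1.017 | 0.22 | 9.2 | 0.939 |
| .2, .3, .4, .5 | 0.35 | 0.15 | 1.029 | 0.29 | 8.1 | 0.936 |
| .6, .45, .3, .2 | 0.3875 | 0.1875 | 1.046 | 0.36 | 9.5 | 0.933 |
| .7, .5, .2, .1 | 0.375 | 0.275 | 1.099 | 0.53 | 10.0 | 0.921 |

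Worked for the last row: 64 × 0.275² = 4.84; 1 + 4.84/49 = 1.099; 0.275 × 1.91 = 0.53. Power with the right slope, under the same assumptions (35 per arm, difference 6.0, residual SD 7), is 0.942.

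**The leftover and the variance increase are one effect.** In the last row, 0.526²/2.80 = 0.099, which is exactly the variance increase in the table. They must not be added together.

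**Simulation.** The model was also fitted to simulated trials with 35 per arm, residual SD 8, residual correlation 0.6 and unstructured covariance (400 runs per scenario; error about 2 points on power and 0.1 on the mean). The true difference was 6.0.
- Slopes .6, .45, .3, .1: the common-slope model adjusted 24 months with a slope of 0.37, the visit-specific model with 0.10. Mean estimates were 6.02 and 6.00, average standard errors 1.99 and 1.92, power 0.84 and 0.87. The gap between the two estimates had an SD of 0.57 points and followed baseline imbalance (correlation −0.94).
- The same slopes with about 16% missing at 24 months: means 5.99 and 6.02, power 0.79 and 0.83.
- Slopes .5, .4, .3, .2: power 0.87 and 0.88.
- Slopes all 0.3: the mean difference between the models was 0.01.

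The first scenario is extreme. It implies an SD of change at 24 months of √(64 × 0.81 + 64) = 10.8, above every value in section 12.2.

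**Cost of the term if it is not needed.** With equal slopes and 70 patients, estimating a separate slope at each visit adds roughly 0.75 × (1 − ρ)/70 to the relative variance of the 24-month contrast, where ρ is the residual correlation. That is 0.8% at ρ = 0.3 and 0.3% at ρ = 0.7.

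**The case against.** Four points can fairly be made for the plan.

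1. *The text is silent; it does not prohibit.* Section 12.4 says only that baseline enters as a covariate. It does not exclude an interaction. This is true. But it lists its model terms and spells out one interaction, so someone programming from it would fit one baseline slope.

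2. *The estimate is not biased.* A reader might infer that the 24-month result will be systematically wrong because it uses the wrong slope. The documents do not support that. Allocation is randomised 1:1, so the contrast is unbiased for any fixed slope, and the simulated means bear this out. Nor is the test shown to be invalid: the misfit enters the estimated residual variance, so the standard error reflects it. This objection stands in full.

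3. *The larger figures fit the plan poorly.* The scenarios with a 5% to 10% increase imply an SD of change of 9.5 to 10.0, against the planning value of 8.0. The one scenario close to 8.0 gives 2.9%. This also stands, so the upper figure is an outer limit and not an expectation.

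4. *Nothing shows that the slopes differ.* No section reports how pre-operative OKS relates to OKS at the separate visits. The premise is conditional. In the mildest scenario the 1.7% loss is also partly offset by the 0.3% to 0.8% cost of the extra terms, leaving a net gain of about 1%.

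**Conclusion.** The point holds as a small gain in precision. Section 12.4 as written fits one baseline slope to four visits spanning 6 weeks to 24 months, although only the last carries the primary objective. If the true slopes differ, the 24-month OKS contrast stays unbiased but is somewhat less precise than the same data allow.

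Under the assumed baseline SD of 8 and residual SD of 7, the loss is about 2% to 3% of variance for slope errors of 0.10 to 0.15, and up to about 10% in scenarios further from the planning SD. Power falls from 0.942 to between 0.939 and 0.921. Against a postulated difference of 6.0, the leftover imbalance is 0.2 to 0.5 points per standard error of imbalance. All these sizes rest on slopes and SDs that the documents do not give. If the slopes are equal, there is no loss to recover. The sample size is unaffected.

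**What to change.** In section 12.4, extend the sentence listing the model terms with *and the interaction between baseline value and time*, for OKS and each continuous secondary score. Make the change before the data are analysed, so that the choice is not made after seeing results.

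It needs no new data. By the evaluation schedule it adds three parameters for OKS (four post-operative visits), two each for EQ-5D, VAS pain and the Forgotten Joint Score (three visits), and one for the Knee Society Score (two visits). If the slopes are in fact equal, the price for OKS is under about 1% in the variance of the 24-month contrast.
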